9.5 Outliers

Outliers will be identified through a review of TLF for investigation by Data Management and Project Management. All outlier data will be included in the analyses presented in this SAP. Any unconfirmed outlier data will be followed up by Project Management.

9.6 Validation Plan

SAS® version 9.3 on the Windows system will be used for all TLF creation. The verification of the outputs, the analysis datasets as well as the review of all programs and macros created specifically for this study, will be conducted as outlined in TRIO Standard Operating Procedures SOP 8.3 “Conduct of Statistical Analysis”, SOP 8.4 “Preparation of Statistical Analysis” and Standard Guidelines SG 8.1 “Validation of Statistical Analysis”.

10. STATISTICAL METHODS OF ANALYSIS

Categorical variables will be summarized in frequency tables, with the counts and percentage of patients in each category. Percentages given in the summary tables will be rounded and thus may not always add up to exactly 100 percent. For continuous variables, summary statistics will include number of patients, mean, standard deviation, first quartile (Q1), median, third quartile (Q3), minimum and maximum values (range).

10.1 Patient Disposition

The patient disposition will be tabulated using the FAS. Frequency count and respective percentages of patients who were in each analysis set (i.e. FAS, Per-protocol, and Safety), and discontinued from treatment and/or study will be summarized by treatment group. The reason for discontinuation (from treatment and/or from study participation where applicable) will be summarized considering the categories specified in the case report forms. Listings of disposition information and analysis population will be provided as well.

Protocol Deviation including eligibility deviations of the inclusion/exclusion criteria will be summarized and listed for FAS, by treatment group.

The stratifications factor (for Phase 2 portion) will also be tabulated by treatment group.

10.2 Demographics and Disease Characteristics

The following demographics and baseline characteristics will be summarized and listed for the FAS by treatment group:

Demographics:

- Age, $INT(Date\ of\ enrollment/randomization - Date\ of\ birth) / 365.25$
 - $INT =$ integer part
 - Since only the year of birth is collected (YYYY), we assume the full date to be 31-Dec-YYYY
- Race
- Ethnicity
- Menopausal Status
- Weight at Baseline
- Height at Baseline
- ECOG Status at Baseline

Disease Characteristics:

- Time from Initial Diagnosis to Randomization
- Primary Tumor Location
- Staging at Initial Diagnosis
- Histopathological Type at Initial Diagnosis
- Histopathological Grade at Initial Diagnosis
- Disease Status at Registration
- Time from Metastatic / Locally Recurrent Disease to Randomization
- Local Estrogen Receptor Status
- Local Progesterone Receptor Status
- Local HER2 Status

10.3 Prior Surgery for Breast Cancer

Number of patients who underwent prior surgeries will be summarized by type and location of surgery. A listing will also be provided.

10.4 Prior Systemic Anti-Cancer Therapy

Number of regimens of prior systemic anti-cancer therapies will be summarized by type and indication. A listing will be provided to show the specifics of the therapies.

10.5 Prior Radiation Therapy

Number of radiation therapies will be summarized by site and indication. A listing will be provided to show the specifics of all reported radiation therapies.

10.6 Medical History

The medical history is coded by the most current version of Medical Dictionary for Regulatory Activities (MedDRA), and will be summarized for FAS by System Organ Class (SOC) and Preferred Term (PT) by treatment group.

10.7 Extent of Exposure

Number of Cycles, Duration of Treatment, Cumulative Dose and Relative Dose Intensity (RDI) will be summarized by treatment for the safety analysis set.

Atezolizumab:

**Statistical Analysis Plan
SNDX-275-0602 (TRIO025)
DM-025-037**

- Number of Cycles: number of cycles having total dose > 0 mg reported
- Duration of Treatment (weeks) = [(Date of last dose - date of first dose) + 21] ÷ 7
- Cumulative Dose (mg) = sum of total dose administered as reported
- Weekly Dose Intensity (mg/week) = (Cumulative Dose) ÷ (Duration of Treatment)
- Planned Weekly Dose Intensity (mg/week) = 1200mg ÷ 3 weeks = 400
- RDI (%) = (Weekly Dose Intensity ÷ Planned Weekly Dose Intensity) × 100

Entinostat:

- Number of Cycles: number of cycles having total dose > 0 mg reported
- Duration of Treatment (weeks) = [(Date of last dose - date of first dose) + 21] ÷ 7
- Cumulative Dose (mg) = sum of total dose administered as reported
- Weekly Dose Intensity (mg/week) = (Cumulative Dose) ÷ (Duration of Treatment)
- Planned Weekly Dose Intensity (mg/week) = (Dose Cohort as assigned in Phase 1b or RP2D in Phase 2) ÷ 3 weeks
- RDI (%) = (Weekly Dose Intensity ÷ Planned Weekly Dose Intensity) × 100

The RDI will be additionally presented categorized (i.e., number and percentage of patients with RDI of < 60%, 60 - < 80%, 80 - < 90%, 90 - < 110%, ≥ 110%).

The number and percentage of patients with dose interruptions/discontinuations or reduced (entinostat/placebo at Phase 2 only), along with their respective reasons will be summarized.

For entinostat/placebo, the compliance will be summarized by visit using the following calculation:

$$\text{Compliance (\%)} = \frac{\text{Number of Tabs taken} + \text{Number of Tabs Returned}}{\text{Number of Tabs Dispensed}} \times 100$$

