9.2 Entinostat

9.2.1 Supply and Storage

Entinostat is a synthetic small molecule bearing the chemical name 3-Pyridylmethyl N-{4-[(2-aminophenyl)carbamoyl]benzyl}carbamate and the molecular formula C₂₁H₂₀N₄O₃, with a molecular weight of 376.41. Entinostat is classified as an antineoplastic agent, specifically functioning as an inhibitor of histone deacetylases that promotes hyperacetylation of nucleosomal histones, allowing transcriptional activation of a distinct set of genes that leads to the inhibition of cell proliferation, induction of terminal differentiation, and/or apoptosis.

Entinostat/placebo is an oral drug supplied by Syndax to the sites as pink to light red (1 mg) or yellow (5 mg) as polymorph B coated tablets. Each tablet contains mannitol, sodium starch glycolate, hydroxypropyl cellulose, potassium bicarbonate, and magnesium stearate as inert fillers. The film coating consists of hypromellose, talc, titanium dioxide, and ferric oxide pigments (red and yellow) as colorants.

Entinostat/placebo is to be stored at controlled room temperature (15°C to 25°C / 59°F to 77°F) in a secure, locked storage area to which access is limited.

Entinostat/placebo is to be protected from light. Entinostat/placebo is not to be exposed to extremes of temperature (greater than 30°C / 86°F or less than 5°C / 41°F). The pharmacist will dispense the investigational material to the patient at appropriate intervals throughout the study in childproof containers.

Entinostat/placebo will be supplied to patients in bottles containing enough pills for a 3-week cycle, plus an additional dose in case tablets are lost.

Please refer to the Pharmacy Manual for complete details regarding supply, storage accountability and destruction Entinostat.

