9.2.2 Dosing and Administration

All patients will self-administer entinostat/placebo PO once weekly on study days 1, 8 and 15 of each 21 day cycle. A new bottle of entinostat/placebo will be dispensed on day 1 of each cycle, regardless of the number of pills remaining in the bottle from the previous cycle.

On study days on which patients receive both entinostat/placebo and atezolizumab, entinostat/placebo is to be taken prior to atezolizumab.

Entinostat/placebo is to be taken on an empty stomach, at least 2 hours after a meal and at least 1 hour before the next meal.

If an entinostat/placebo dose is missed, it may be taken up to 48 hours after the scheduled dosing time. If it is not taken within the 48 hour window, the dose should not be taken and will be counted as a missed dose. The patient should take the next scheduled dose per protocol. Missed doses should be noted as such on the patient drug diary and in the eCRF.

If entinostat/placebo is vomited, dosing should not be re-administered but instead the dose should be skipped.

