9.5 Entinostat Compliance

Treatment compliance to entinostat will be assessed at the end of each cycle. Patients will complete a diary to document their weekly intakes. They will be instructed to return all unused drugs (partially used and empty containers) and their diary at each visit. Site staff will perform accountability of the returned drug and will assess patient compliance. Site staff must ensure that the patient clearly understands the directions for self-medication and follows the schedule.

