3.1 Phase 1b Dose Determination Phase

This study phase employs a classical 3+3 design, with the determination of DLT and the MTD or RP2D at cycle 1 based on the combination of entinostat (at the dose of 5mg, 3mg or 2mg weekly) with atezolizumab at a fixed dose of 1200 mg iv. Six patients will need to be treated in a dose level for it to be considered MTD or the RP2D. The recommended dose for Phase 2 investigation will be the higher of either 2, 3, or 5mg weekly PO that results in less than a 33% incidence of DLT.

Note: Based on evaluation of the safety and tolerability data gathered during the dose determination phase together with data from other clinical trials, it may also be decided that accrual will take place at an alternate dose level or dosing schedule via a protocol amendment.

Up to 18 patients are expected to be enrolled in the Dose Determination Phase of the study.

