6.11.3 Date of Last Dose

The date of last dose (of study drug) is derived as the last date when a nonzero and nonmissing dose of study drug is administered.

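### SAP 10.7 scores a fully dosed entinostat patient at 180% to nearly 300% relative dose intensity, and its compliance formula gives 100% to a patient who takes no tablets and returns them all

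*SAP*

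**What the plan says.** Protocol 9.2.2 gives the schedule: "All patients will self-administer entinostat/placebo PO once weekly on study days 1, 8 and 15 of each 21 day cycle". SAP 3.1 names the cohorts in the same unit: "entinostat (at the dose of 5mg, 3mg or 2mg weekly" in combination with atezolizumab.

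SAP 10.7 then defines, for entinostat:

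- planned intensity: "Planned Weekly Dose Intensity (mg/week) = (Dose Cohort as assigned in Phase 1b or RP2D in Phase 2) ÷ 3 weeks"
- duration, with the same formula as for atezolizumab: "Duration of Treatment (weeks) = [(Date of last dose - date of first dose) + 21] ÷ 7"
- RDI as actual over planned weekly intensity, tabulated as < 60%, 60 to < 80%, 80 to < 90%, 90 to < 110% and ≥ 110%.

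SAP 6.11.3 fixes the end date in the duration formula: it is "derived as the last date when a nonzero and nonmissing dose of study drug is administered".

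For entinostat/placebo, SAP 10.7 adds that "the compliance will be summarized by visit using the following calculation": tablets taken plus tablets returned, divided by tablets dispensed, times 100. Protocol 9.2.1 describes what is dispensed: "Entinostat/placebo will be supplied to patients in bottles containing enough pills for a 3-week cycle, plus an additional dose in case tablets are lost". Protocol 9.5 says of patients: "They will be instructed to return all unused drugs (partially used and empty containers) and their diary at each visit". The same section lists accountability of returned drug and assessment of compliance as two tasks for site staff.

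**The concern.** The entinostat block repeats the structure of the atezolizumab block. Dividing by 3 weeks and adding 21 days suit a drug given once per 3-week cycle. They do not suit one given every week.

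An RDI is useful only if full dosing reads 100% whatever the time on treatment. Here it would start well above 100% and rise with each cycle, so it would mix dose delivery with treatment duration. Moderate under-dosing of the experimental drug would fall in the same category as perfect dosing.

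The compliance formula looked wrong for a different reason. Returned tablets count towards the score, so it shows whether tablets are accounted for and not whether they were taken.

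At stake are the tables that show whether entinostat could be delivered at its assigned dose alongside atezolizumab, and whether patients took it.

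**Working it through.** **The plan's own figure.** For atezolizumab, SAP 10.7 gives 1200 mg ÷ 3 weeks = 400 mg/week, which reproduces. With n full cycles, last dose minus first dose is 21(n − 1) days, duration is 3n weeks, and RDI = (1200n ÷ 3n) ÷ 400 = 100% for every n. The formulas work for that drug.

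**Entinostat, general form.** Let d be the weekly dose, k the number of doses taken at d, and w the weeks from first to last dose taken.

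- Duration = (7w + 21) ÷ 7 = w + 3 weeks
- Actual intensity = kd ÷ (w + 3)
- Planned intensity = d ÷ 3
- RDI under the SAP = 3k ÷ (w + 3), the same at 5, 3 and 2 mg

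With planned intensity d and a 7-day tail, RDI = k ÷ (w + 1).

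**Full dosing.** Here k = 3n and w = 3n − 1, so the SAP gives 9n ÷ (3n + 2).

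| Cycles | SAP as written | Only the ÷ 3 removed, 3n ÷ (3n + 2) | Both lines changed |
|---|---|---|---|
| 1 | 9/5 = 180% | 3/5 = 60% | 100% |
| 2 | 18/8 = 225% | 6/8 = 75% | 100% |
| 4 | 36/14 = 257% | 12/14 = 86% | 100% |
| 8 | 72/26 = 277% | 24/26 = 92% | 100% |

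The first column tends to 300%. Changing only the tail to 7 days would give a constant 300%.

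**Missed doses over 4 cycles** (12 scheduled; first and last taken, so w = 11 and the SAP gives 3k/14).

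| Doses taken | SAP RDI | SAP category | Corrected, k/12 |
|---|---|---|---|
| 12 | 257% | ≥ 110% | 100% |
| 11 | 236% | ≥ 110% | 92% |
| 6 | 129% | ≥ 110% | 50% |
| 5 | 107% | 90 to < 110% | 42% |
| 4 | 86% | 80 to < 90% | 33% |
| 3 | 64% | 60 to < 80% | 25% |
| 2 | 43% | < 60% | 17% |

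If the six doses are numbers 1, 3, …, 11, then w = 10, the SAP gives 18/13 = 138%, and the corrected value is 6/11 = 55%.

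**Dose reduction.** Assigned 5 mg, reduced to 3 mg from cycle 2, four cycles, no missed doses: cumulative dose is 15 + 27 = 42 mg. The SAP gives (42 ÷ 14) ÷ (5 ÷ 3) = 180%. Corrected: (42 ÷ 12) ÷ 5 = 70%.

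**Compliance.** Assume one 5 mg tablet per dose, so a bottle holds three doses and one spare, 4 tablets.

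| Taken | Returned | SAP compliance | Taken ÷ scheduled (3) |
|---|---|---|---|
| 3 | 1 | 100% | 100% |
| 1 | 3 | 100% | 33% |
| 0 | 4 | 100% | 0% |
| 3 | 0 (spare lost) | 75% | 100% |

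The third row does not depend on the 4-tablet assumption: none taken and all returned gives 100% for any number dispensed.

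**The case against.** **The wording may only be loose.** SAP 10.7 counts cycles with a non-zero total dose, and the exposure listing is by visit, which suggests cycle-level records. If the last date meant the start of the last cycle and the dose cohort meant the cycle total, full dosing would give exactly 100%. That needs both readings at once. The first alone gives 300%, and the second alone gives 60% after one cycle. SAP 6.11.3 contradicts the first and SAP 3.1 the second. It is plausible that a template was only partly adapted, but the formulas as written still give wrong results.

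**The low rows are unlikely.** A footnote to protocol Tables 9-1 and 9-2 ends study drug if more than half the doses are missed in any 6 weeks. Patients with 2 to 5 of 12 doses should therefore not normally still be on drug at dose 12. This stands: those rows could arise only from non-adherence or deviation. They serve here only to show that some severe under-dosing would still be visible.

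**The RDI error would be noticed.** An RDI of 180% or more, on a drug whose dose cannot be raised above the assigned level, should stand out in the dry runs of SAP 9.1. That is likely. The compliance error is harder to see, because 100% is an expected value. Cumulative dose, number of cycles and recorded missed doses would expose a patient who took nothing, but the compliance table itself would not.

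**The replacement formulas have limits.** RDI up to the last dose taken ignores doses missed after it. That follows from the SAP's own last-dose definition, and discontinuations are tabulated separately. A tablet ratio weights doses unequally if the dose is reduced within an interval. Assuming 3 mg is three 1 mg tablets, one 5 mg and two 3 mg doses make 7 tablets; missing the 5 mg dose gives 6/7 = 86%, and missing a 3 mg dose gives 4/7 = 57%. This stands, but only for such intervals.

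**Conclusion.** The concern holds. Both entinostat metrics in SAP 10.7 are wrong as written. Full dosing gives an RDI of 180% after one cycle, rising towards 300%. Over four cycles at an unreduced dose, half dosing and full dosing fall in the same category. The compliance score does not measure intake and can rank a patient who took nothing above one who took every scheduled dose.

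The RDI results rest on weekly dosing as both documents describe it and on the SAP's definition of last dose. The 75% compliance example also assumes one tablet per dose.

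The damage is limited to descriptive exposure, tolerability and adherence tables in the safety set. The PFS test, its type I error and its power do not use these quantities. Cumulative dose, number of cycles and dose changes are reported separately and stay valid. This should be corrected before the tables are programmed, but it does not threaten the trial's primary conclusion.

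**What to change.** In SAP 10.7, for entinostat/placebo:

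1. Set planned weekly dose intensity (mg/week) to the assigned weekly dose (dose cohort or RP2D), with no division by 3.
2. Set duration of treatment (weeks) to (date of last dose − date of first dose + 7) ÷ 7. Make changes 1 and 2 together.
3. Define compliance (%) as tablets taken ÷ tablets scheduled in the interval × 100. Exclude the spare dose from the denominator, use the dose in force at each scheduled dose after documented reductions, and leave out doses withheld under a documented protocol-directed hold. Report not applicable if none were scheduled. Where the dose changes within an interval, counting doses instead of tablets avoids unequal weighting. State how a vomited dose counts.
4. Keep the present compliance formula only if it is relabelled as tablet accountability.

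Excluding protocol-directed holds is a convention; what matters is to state it in advance. The atezolizumab formulas need no change.

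The cost is a few lines in the SAP and the programming specification. The inputs appear to be collected already: the present formula uses tablets taken, returned and dispensed; protocol 9.2.2 has missed doses recorded in the diary and eCRF; and SAP 10.7 already plans to summarise interruptions and reductions with their reasons.

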Phase 1b (Dose Determination): This study phase employs a classical 3+3 design, with the determination of DLT and the MTD or RP2D based on the combination of entinostat with atezolizumab in C1. Six patients will need to be treated in a dose level for it to be considered MTD or the RP2D. The recommended dose for Phase 2 investigation will be the higher of either 2, 3 or 5 mg weekly PO that results in less than a 33% incidence of DLT. The final determination of the optimal dose for further use will consider both acute and cumulative toxicities; the incidence of required dose delays, reductions, and discontinuations; and the overall facility of administration in clinical practice.

The initial 3-6 patients will receive entinostat at a starting dose of 5 mg (Dose Group 1) on D1, D8, and D15 along with atezolizumab 1200 mg via intravenous (IV) infusion on D1 of each 21-day cycle.

If the 5 mg dose exceeds the MTD, then a 3 mg dose of entinostat (Dose Group -1) will be evaluated in the same manner. If the -1 dose level exceeds the MTD, then a 2 mg dose of entinostat (Dose Group -2) will be evaluated. Based on evaluation of the safety and tolerability data gathered during the dose determination phase together with data from other clinical trials, it may also be decided that accrual will take place at an alternate dose level or dosing schedule via a protocol amendment.

Patients who experience a DLT will be allowed to remain on study if they meet the following criteria; (1) the investigator believes it is appropriate for patients to remain on study (2) the event has resolved and no longer meets the definition of DLT and (3) the timeline for resolution falls within the guidelines for dose delays ([Section 9.10](#)).

Phase 2 (Expansion): The efficacy and safety of entinostat in combination with atezolizumab will be evaluated using the RP2D identified in the Dose Determination Phase. In this randomized, placebo-controlled, double-blind study phase, 70 patients will be randomized in a 1:1 fashion to atezolizumab + entinostat versus atezolizumab + placebo. The randomization will be stratified by geographic location (US vs. rest of world).

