9.10.1 Entinostat

In Phase 1b, dose delays, but not dose reductions will be allowed for entinostat during Cycle 1.

If a dose reduction is required during Cycle 1, the patient will be taken off study. Dose delays for reasons other than toxicities definitely or possibly related to entinostat should be avoided as much as possible during Cycle 1.

In Phase 2, both dose delays and dose reductions will be allowed as described below. Once the entinostat dose is reduced, it cannot be re-escalated.

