9.10.1.1 Non-hematologic Toxicity at Least Possibly Related to Entinostat

The rules outlined in [Table 9-1](#) are to be followed for the management of non-hematologic toxicities that are definitely or possibly due to entinostat alone, with toxicities graded by the Investigator according to the NCI, CTCAE, version 4.03. Note: No dose reduction is allowed during the first study treatment cycle in phase 1b.

Table 9-1 Non-hematologic Toxicity: Dose Modifications for Entinostat

Toxicity	Dose modifications
Grade 4	
Administer symptomatic remedies/ start prophylaxis.
 
Hold¹ dose until recovery to Grade 1 or baseline under the following directions.
 
1. If recovered within 4 weeks of onset (ie: ≤3 missed doses) , resume study drug as follows:
• If receiving 5 mg, restart study drug at 3 mg• If receiving 3 mg, restart study drug at 2 mg• If receiving 2 mg, discontinue study treatment2. If dose is held for 4 consecutive weeks, permanently discontinue study drug.
Grade 3	
Administer symptomatic remedies/ start prophylaxis.
 
Hold¹ dose until recovery to Grade 1 or baseline under the following directions:
 
1. If recovered by next scheduled dose, resume study drug at prior dose. If not recovered by next scheduled dose, continue to hold the dose.2. If recovered within 2-4 weeks (i.e. missed 3 or less doses) resume study drug as follows:
• If receiving 5 mg, restart study drug at 3 mg.• If receiving 3 mg, restart study drug at 2 mg.• If receiving 2 mg, discontinue study treatment. 
If dose is held for 4 consecutive weeks, permanently discontinue study drug.

Recurrence of the same Grade 3 toxicity despite dose reduction	
Administer symptomatic remedies / start prophylaxis.
 
If receiving 2 mg, permanently discontinue study drug. Otherwise, hold¹ dose until recovery to Grade 1 or baseline.
 
1. If recovered within the next 2 scheduled doses, resume study drug as follows:
• If receiving 5 mg, restart study drug at 3 mg• If receiving 3 mg, restart study drug at 2 mg2. If the same ≥Grade 3 event recurs (i.e., 3 occurrence) despite entinostat dose reduction to 2 mg, as described above, discontinue study drug.

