9.10.1.2 Hematologic Toxicity at Least Possibly Related to Entinostat

The guidelines in [Table 9-2](#) will be followed for determining the timing of cycles based on hematologic status at the time of planned dosing. Note: No dose reduction is allowed during the first study treatment cycle during phase 1b.

Table 9-2 Hematologic Toxicity: Dose Modification for Entinostat

Toxicity	Dose modifications
≥Grade 3 neutropenia, ≥Grade 3 uncomplicated thrombocytopenia, or Grade 2 complicated thrombocytopenia	Administer symptomatic remedies/ start prophylaxis. Hold dose ¹ until recovery to Grade 1 or study baseline using the following directions: 
1. If recovered by next scheduled dose, resume study drug at prior dose. If not recovered by next scheduled dose, hold the dose.2. If recovered within the next 2-4 weeks (i.e. missed 3 or less doses) resume study drug as follows:
• If receiving 5 mg, restart study drug at 3 mg.• If receiving 3 mg, restart study drug at 2 mg.• If receiving 2 mg, permanently discontinue study drug.3. If not recovered within 4 weeks (i.e. 4 doses missed), permanently discontinue study drug.
Recurrence of the same hematologic toxicity	Administer symptomatic remedies/ start prophylaxis. If receiving 2 mg, permanently discontinue study drug. Otherwise, hold ¹ dose until recovery to Grade 1 or baseline. 
1. If recovered within the next 2 scheduled doses, resume study drug as follows:
• If receiving 5 mg, restart study drug at 3 mg• If receiving 3 mg, restart study drug at 2 mg2. If the same ≥Grade 3 event recurs (i.e., third occurrence) despite entinostat dose reduction to 2 mg, as described above, discontinue study drug.

¹ If greater than 50% of doses are missed during any 6 week period, discontinue from study drug treatment.

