13.5.4 Extent of Exposure

The overall duration of study treatment administration and number of cycles initiated will be tabulated for each patient and summarized for each study phase. For each patient, the cumulative doses administered (in mg) of both entinostat and atezolizumab will be calculated. These data will be further summarized for each dose cohort (or treatment arm) by calculating the mean, standard deviation, median, and range of these values. The number and proportion of patients with one or more dose modifications (i.e., reduction or delay) will be tabulated along with the reason for modification.

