TEAEs with Action Taken as Treatment delayed/interrupted for Entinostat	Safety	Summary by SOC and PT for each treatment group.
TEAEs with Action Taken as Treatment delayed/interrupted for Atezolizumab	Safety	Summary by SOC and PT for each treatment group.
TEAEs with Action Taken as Dose Reduced	Safety	Summary by SOC and PT for each treatment group. (For Phase 2 only)

**Statistical Analysis Plan
SNDX-275-0602 (TRIO025)
DM-025-037**

Title	Population	Description
for Entinostat		
TEAEs Leading to Treatment Discontinuation	Safety	Summary by SOC and PT for each treatment group.
TEAEs Leading to Treatment Discontinuation	Safety	Summary by PT for each treatment group ordered by frequency.
SAE	Safety	Summary by SOC and PT for each treatment group.
AEs Leading to Death	Safety	Summary by SOC and PT for each treatment group.
Laboratory Values	Safety	Summary of each laboratory parameter at baseline, minimum post baseline value, maximum post baseline value, average post baseline value and last post baseline value for each treatment group. In addition, shift tables will be presented.
ECOG Performance Status	Safety	Summary of ECOG performance status at each baseline, minimum post baseline value, maximum post baseline value, last post baseline value for each treatment group. In addition, a shift table will be presented.
Vital Signs	Safety	Summary of descriptive statistics for each vital sign measurements will be done for baseline value, minimum post baseline value, maximum post baseline value, average post baseline value, and last post baseline value for each treatment group.
ECG	Safety	Tabulate the frequency and percentage of patients according to findings reported at each time point for each treatment group.
Prior and Concomitant Medications	Safety	Tabulate the frequency and percentage of patients according to generic name. Summary will be presented separately for prior medications and

**Statistical Analysis Plan
SNDX-275-0602 (TRIO025)
DM-025-037**

Title	Population	Description
		concomitant medications.
Anticancer Therapy Received after end of study treatment	FAS	Tabulate the frequency and percentage of patients according to type of anticancer therapy received after end of study treatment.

¹ Separate tables to be produced based on per-protocol analysis set if needed.

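### The SAP limits its dedicated entinostat dose-reduction summaries to Phase 2, although Phase 1b reductions are barred only in Cycle 1 and the protocol tabulates reductions without a phase limit

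*SAP*

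**What the plan says.** **SAP.** Section 10.7 summarizes, with reasons, the patients with "dose interruptions/discontinuations or reduced (entinostat/placebo at Phase 2 only"). In section 11.1, the table of treatment-emergent events whose action was an entinostat dose reduction is described as "Summary by SOC and PT for each treatment group. (For Phase 2 only"). The Study Drug Exposure table in the same section also covers interruptions, discontinuations and reductions, but names no phase.

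**Protocol, when reductions may occur.** Section 9.10.1 states: "In Phase 1b, dose delays, but not dose reductions will be allowed for entinostat during Cycle 1". The note introducing the non-hematologic rules says "No dose reduction is allowed during the first study treatment cycle in phase 1b", and the note introducing the hematologic rules says "No dose reduction is allowed during the first study treatment cycle during phase 1b".

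**Protocol, what reductions are used for.** The Phase 1b paragraph of 6.1 says that the final choice of dose takes account of "the incidence of required dose delays, reductions, and discontinuations", among other things.

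**Protocol, what is tabulated.** Section 13.5.4 plans that "patients with one or more dose modifications (i.e., reduction or delay) will be tabulated", together with the reason. Section 13.5.1 presents Dose Determination tabulations by dose cohort and overall.

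**The concern.** The SAP appears to carry a Cycle 1 ban over to the whole of Phase 1b. If reductions can occur from Cycle 2, a dose cohort may contain patients who passed Cycle 1 at the assigned dose and were later brought down. The protocol treats that frequency as relevant to the dose taken forward. SAP 5.4.1 plans a safety analysis at the end of the dose determination phase, which is where a reader would look for it. The SAP gives no reason for being narrower than the protocol.

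What is at stake is a descriptive count: for each Phase 1b dose cohort, how many patients were reduced and why. No hypothesis test or efficacy estimate depends on it.

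**Working it through.** The plan states no figure to reproduce, so the check is a comparison of texts, with one small calculation.

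**1. Is the restriction about phase, or only about product?** Read alone, the parenthesis in SAP 10.7 might mean only that reductions apply to entinostat/placebo, since atezolizumab is never reduced (Protocol 9.10.2). The 11.1 table settles this. Its title already names entinostat, and it is still marked for Phase 2 only. The restriction is about phase.

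**2. Can a Phase 1b patient be reduced?** Three places in Protocol 9.10.1 confine the ban to the first cycle, which would be pointless if it covered every cycle. The Phase 1b text of the synopsis also foresees later reductions for cumulative toxicity in patients who continue treatment. The permission is implied, not explicit: 9.10.1 expressly allows reductions only when it turns to Phase 2. The implication is nevertheless clear.

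**3. Which planned outputs would show a Phase 1b reduction?**

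| Output | Phase limit | What it would give |
|---|---|---|
| SAP 10.7 count of reduced patients, with reasons | Phase 2 only | Nothing for Phase 1b |
| SAP 11.1 table, entinostat dose reduced | Phase 2 only | Nothing for Phase 1b |
| SAP 11.1 Study Drug Exposure table | None stated | Possibly a count; conflicts with 10.7 |
| SAP 10.9.2 tabulation and 11.1 TEAEs Overview | None stated | Reduced pooled with delayed or interrupted |
| SAP 11.1 table, entinostat delayed/interrupted | None stated | The hold that usually precedes a reduction |
| SAP 11.2 listings (exposure by visit, all AEs, entinostat dose reduced) | None stated | Individual cases |

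No row clearly gives a separate count, with reasons, of reduced patients per Phase 1b cohort.

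**4. Would the DLT table catch them instead?** Protocol 9.6 also counts as a DLT the inability to receive more than 60% of planned entinostat over the first two cycles. Take a patient in the 5 mg cohort with a full Cycle 1, reduced to 3 mg in Cycle 2. The planned dose is 6 × 5 = 30 mg.

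- No missed dose: (3 × 5 + 3 × 3)/30 = 24/30 = 80%. Not a DLT on this criterion.
- One missed dose in Cycle 2: (15 + 2 × 3)/30 = 21/30 = 70%. Not a DLT on this criterion.
- Two missed doses in Cycle 2: (15 + 1 × 3)/30 = 18/30 = 60%, which is not more than 60%. A DLT on this criterion.

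The DLT table would therefore catch some Cycle 2 reductions and miss others. A reduction first made in Cycle 3 or later is outside this criterion.

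**The case against.** The strongest reply is that little is lost.

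- **Other outputs remain.** Several tabulations and listings carry no phase limit, as the table above shows. The TEAEs Overview plainly covers Phase 1b, because its description also mentions the Phase 1b DLT rate.
- **Reductions usually follow a hold.** In Protocol Tables 9-1 and 9-2 the routes to a lower dose begin with holding the drug, and interruptions are tabulated for both phases. A reduced patient would ordinarily appear as an interrupted one. What disappears is the split between held and resumed and held then reduced. Exceptions are possible, such as a Grade 4 event that recovers before the next dose, or a more cautious investigator decision under 9.10.
- **The dose decision does not rest on this table.** The MTD rests on DLTs (Protocol 9.7). The RP2D is set in discussion among the Sponsor, Medical Monitor and Phase 1b investigators (9.8), with safety data on continuing patients reviewed as they arrive. With at most 18 open-label patients, cases can be read one by one.

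All of this stands. It also rules out stronger readings. A reader might infer that Phase 1b cohorts would be reported as having no reductions, that only a listing would survive, or that the RP2D decision would be deprived of the information. The documents support none of these: the SAP omits a dedicated count and does not report zero, tables as well as listings remain, and nothing shows that the decision-makers depend on the SAP table.

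The reply does not remove the contradiction. SAP 10.7 disagrees with Protocol 13.5.4 and with the SAP's own Study Drug Exposure table, and a programmer cannot follow both SAP statements for Phase 1b.

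**Conclusion.** The point holds as a minor reporting inconsistency. Two SAP entries exclude Phase 1b from the dedicated reduction summaries, against a protocol that plans the tabulation without a phase limit and names the incidence of reductions as a dose-selection consideration. The effect is limited to one descriptive item, the count of reduced patients with reasons per dose cohort, in up to 18 patients.

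This rests on two readings. Reductions in Phase 1b are taken to be permitted from Cycle 2 because the ban is written for Cycle 1 only. The optimal-dose sentence in 6.1 is read as bearing on the RP2D because it directly follows the rule for the recommended Phase 2 dose. How many patients would actually be reduced cannot be known from the documents.

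**What to change.** In SAP 10.7, remove the Phase 2 restriction from the summary of reductions and keep the limit to entinostat/placebo. In SAP 11.1, remove the Phase 2 restriction from the table of events leading to entinostat dose reduction. State that reductions are shown with reasons by assigned dose cohort for Phase 1b (Cycle 2 onward) and by treatment arm for Phase 2. This also brings 10.7 into line with the Study Drug Exposure table.

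The cost is two deletions and one clarifying sentence. The listings already planned draw on the same data, and the Phase 2 program can be run on Phase 1b. Only descriptive reporting changes; every dosing rule in the protocol stays as it is.
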